## Data Management

We anticipate limited missing data and out of range responses by using the internet-based assessment, with phone calls to check with non-responders and mailed short-forms completed if necessary, as was the case in our previous research. We have established a minimum, abbreviated set of forms that provide primary and secondary outcomes (CTXD, HCA, PHQ-8). Assessment programming will set parameters for allowable responses and will return responders to items either missed or outside range, with an option to click a 'choose not to respond' box. Validity checks will also be programmed to flag responses that are markedly inconsistent and may be invalid. Outliers will be identified and sent to the [name] and the mPIs to determine whether clinical response is needed. The mPIs will be notified and will contact a participant if validity seems questionable. They will assure that the participant personally completed the items and is cognitively capable of responding. In the past this has occurred only rarely, less than 1% of the time. A second level of flagging will occur when depression responses indicate severe depression, as we expect 2% of assessments. In these cases, the Project Manager will notify [name]. The Project Manager's data will be coded without names and [name] will decode these.

Programming will provide for calculation of summary scores and data will be routinely downloaded to a project database. The Statistician will examine distributions for normality (e.g., outliers, skewness) and conduct appropriate transformations or category coding if distributions are non-normal. When data cleanup is complete, all files will be merged into a project database. The project database and all data collection, analysis, and storage will be maintained at the Coordinating Center. No study data will be maintained at the consortium sites.

## Endpoints

The primary endpoints to be evaluated for the above hypotheses are CTXD (distress) and HCA-cardio. The primary and secondary endpoints for the study will be defined as binary outcomes. Participants will qualify for analysis of a particular endpoint if they meet eligibility at their baseline response for that endpoint (CTXD  $\geq 0.9$  or HCA-cardio  $<80\%$  [primary endpoints], or HCA-cancer  $<80\%$  [secondary endpoint], PHQ-8 score  $\geq 10$ ). Some participants will contribute to both primary endpoint analyses, and others to none or one. Similar conditional analyses will be carried out for the secondary endpoints. Stepped-care telehealth will be introduced based on PRO assessed at 6-weeks, then short term outcomes will be assessed after 3 months and delayed or sustained effects will be assessed at 1 year.

### Primary Hypothesis

**Aim 1:** Among HCT survivors with poor health care adherence to cardiometabolic or subsequent malignancy surveillance and/or elevated cancer-related distress, determine the impact of a patient-centered, self-management stepped care program compared to an active control group provided access to HCT survivorship best practices.

**Hypothesis 1:** Participants with elevated cancer-related distress or poor health care adherence who receive the stepped care program will report reduced distress, and improved health care adherence for cardiometabolic or subsequent malignancy surveillance at 12 months when compared to controls.

### Secondary Hypotheses

**Aim 2:** Determine characteristics of intervention participants who require telehealth stepped care at 6-weeks.

**Hypothesis 2:** Characteristics of intervention arm participants at the 6-week interim assessment who require telehealth stepped care because they 1) do not meet criteria for adequate knowledge of cardiometabolic risks, or 2) do not report improved distress, or 3) have not logged in to the online program will include those with higher depression or distress scores at baseline, more health care barriers at baseline, age 70+ years, male sex, people of color, lower income and education.

**Aim 3:** Determine resources that would be needed to sustain the intervention as a national HCT survivorship program if implemented through the CIBMTR//NMDP.

### Primary Endpoint Tests of the Specific Aims

#### Hypothesis 1

Participants with elevated cancer-related distress or poor health care adherence who receive the stepped care program will report reduced distress, and improved health care adherence for cardiometabolic surveillance at 12 months when compared to controls.

### Power Calculations

As described in Table 3, we expect to enroll a total of 492 subjects in order to attain the 197 and 239 participants needed to meet eligibility criteria for Group 1 randomization and inclusion in the intervention vs. control arm analyses of the 2 primary outcomes: dichotomous CTXD and cardiac HCA outcomes, respectively (some will be eligible for more than one). Among these, we estimate that 71 and 86 per arm will be available for analyses after the 12-month evaluation, respectively. Assuming control arm rates of events similar to or higher than those observed in the preliminary data from the INSPIRE study, these numbers of participants will allow us to detect a minimum relative risk of success for the intervention arm vs. the control arm of 1.9 for the CTXD and for the HCA-cardio endpoints, with 80% power and two-sided  $\alpha=0.025$  for each comparison ( $\alpha=0.05/2 = 0.025$  to conserve overall  $\alpha=0.05$ ). For evaluation of the continuous versions of the outcomes, we will have at least 80% power to detect a minimum effect size of 0.52, and 0.47 for the CTXD and HCA-cardio outcomes, respectively ( $\alpha=0.025$  for each).

Table 3. Sample size calculations for Aim 1 primary outcomes, 80% power

### Analysis Plan for Hypothesis 1

The primary endpoints to be evaluated for hypothesis 1 are distress score (CTXD) and the proportion of HCA-cardio within the past 12 months as reported on the HCA and will be defined as binary outcomes.

Participants will meet the primary endpoint for lack of distress if they score <0.9 on the CTXD. They will

meet the HCA-cardio endpoint if their percent of recommended screenings obtained within the past 12 months is  $\geq 80\%$ . The number and pattern of missing variables will be summarized and assessed to understand potential biases. If attrition is greater than 10% before the 12-month follow-up, we plan to utilize multiple imputation of the primary outcome and to carry out sensitivity analyses of the impact of missing data on the comparisons between study arms.[173]

For Hypothesis 1, the two primary endpoints, evaluated at the 12-month time point among the subjects identified at baseline as impaired for that particular endpoint criteria will each be compared between study arms as intent to treat analyses using standard logistic regression analyses, adjusted for cancer center and utilizing a two-sided  $\alpha=0.025$  level of significance to preserve type I error at 0.05 overall for the two primary endpoints. If other factors appear to be imbalanced between study arms, we will adjust analyses for those factors. Secondary analyses will evaluate depression alone, a PHQ-8 score  $\geq 10$  (essentially a subset of those with distress) and HCA-cancer in a similar manner as carried out for the primary endpoints. Continuous versions of the tests comprising the primary and secondary endpoints using linear regression models as well as adjusting or stratifying on engagement with the intervention (viewing at least 3 pages of the online program or completing telehealth calls) will also be carried out. Assumptions regarding normality of the outcomes will be assessed, although examination of outcomes in preliminary data suggests this is a reasonable assumption, with no significant skew in the distributions. If assumptions are not met, appropriate transformations will be implemented or alternative methods explored (e.g. non-parametric methods).

### Hypothesis 2

Characteristics of intervention arm participants at the 6-week interim assessment who require telehealth stepped care because they 1) do not meet criteria for adequate knowledge of subsequent malignancy and cardiometabolic risks, or 2) do not report improved distress, or 3) have not logged in to the online program will include those with higher depression or distress scores at baseline, more health care barriers at baseline, age 70+ years, male sex, people of color, lower income and education.

### Analysis Plan for Hypothesis 2

Among subjects in Group 0 and Group 1 intervention arms, we will define the endpoint as a binary indicator of whether the individual required telehealth stepped care at the 6-week time point. We plan to use generalized linear models to evaluate associations between patient characteristic variables and likelihood of stepped care. Variables to be examined include age (<70 vs. 70+ years), sex, race/ethnicity (White non-Hispanic vs. Non-White or Hispanic), income ( $<\$40,000$  vs.  $\$40,000$  per year) and education (college graduate yes/no), PHQ8 depression  $>16$ , and Barriers to HCA  $> 0.45$ . The need for telehealth stepped care is not likely to be a rare event (rare being  $<10\%$ ) and thus odds ratios from a logistic regression model would not be good approximations of the relative risk (RR). Therefore, rather

	CTXD	HCA-Cardio	
Enroll/Consent/complete baseline	492	492	
T1: Eligible for specific endpoint	197	239	
3 mo. voluntary withdraw or mortality/illness (4%)	[8]	[10]	
3 mo. non-responders, able to respond at 12 mo. (15%)	[30 eligible for T4]	[36 eligible for T4]	
T3: 3 mo. completers (81%)	160	194	
T4: 12 mo. potential cohort	189	229	
12 mo. voluntary withdraw or mortality/illness (5% of T4)	[9]	[11]	
12 mo. non-responders (20% of T4)	[38]	[46]	
12 mo. completers (75% of T4, 72% of T1)	142	172	
	[71/arm]	[86/arm]	

than logistic regression we will likely use a log-link with Poisson error structure and robust sandwich variance estimates to directly estimate the more interpretable RR.[173] A multivariable model will be established using single-variable and step-up and step-down procedures with a liberal p-value for inclusion in the model ( $p<0.2$ ). Factors identified as significantly ( $p<0.05$ ) associated with the need for telehealth stepped care will be examined and based on the magnitude of the RR estimate and the prevalence of the particular patient characteristic, we will similarly examine indicators of response to the telehealth care based on continuous primary endpoints in that subgroup. This will establish a profile of types of survivors for whom modified approaches to care may be beneficial.

### Aim 3 and Plan for Aim 3

Determine resources that would be needed to sustain the intervention as a national HCT survivorship program if implemented through the CIBMTR/NMDP.

This is a descriptive aim defining costs and resource requirements. Data relevant to resource utilization (costs) and methods of collection are described in section 8.3 Cost and Resource Tracking. All costs associated with the intervention and, separately, the control arms of the study for the Group 0 and Group 1 subjects in the study will be summed and standardized to per person costs. We will use these amounts to calculate an incremental cost ratio for the online intervention program and telehealth intervention component compared to the control cost, similar to the method described by Mandelblatt et al.[171, 172] The costs of maintaining the various components of the program, relative to their use, will be calculated separately for those in the Group 0 and 1 intervention arms, specific to maintaining the social media site, the internet program, and the telehealth calls (Group 1 only) relative to the number of participants using those components among intervention participants.

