This protocol is a 12-site multicenter RCT (N=492), with Seattle as the prime site, partnering with transplant centers in Ohio, Minnesota, Wisconsin, Michigan, Massachusetts, Pennsylvania, New York, Florida, Kansas, Illinois, and Texas. This provides age, region and rural/urban diversity. Participants randomized to the intervention will receive immediate access to the tailored online program, with options for social-media, adding stepped care self-management calls for those not improving by a 6-week interim assessment for those in group 1. Control participants will receive access to a website that provides annotated links to publicly available HCT and cancer websites as well as delayed internet site access. Outcomes will be assessed at 6 weeks, 3 months and 12 months.

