### 7.0 PLAN OF TREATMENT

#### Intervention Selection and Approach

The CIBMTR data registry contains 3765 potentially eligible 2-5 year survivors including 14% minorities from the 13 participating centers. The study Biostatistician will develop a Statistical Analysis Software (SAS) program for random selection of potentially eligible participants with oversampling of minorities (initially all eligible minority cases will be approached) until a minimum of 15% of those randomized are minority race or

ethnicity. The remaining non-minority survivors will be randomly ordered. Each participating center will be sent their randomized approach lists in blocks of 25 cases. Based on our previous INSPIRE enrollment experience with similar eligibility, we found that 26% of cases were not eligible after further screening. We project that we will enroll and randomize 51% of eligible non-minority survivors and 40% of minority survivors. Thus we expect we will approach approximately 1358 (36%) of potentially eligible cases, with 26% not eligible after approach, to achieve our total projected enrollment N=492 to the randomized study.

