First contact will be made with a letter of approach from the site PI and Study Coordinator. The letters of approach from the consortium sites will request permission to provide contact information to NMDP as the follow-up coordinators and to Fred Hutch as the Coordinating Center. Survivors who have opted out of contact or are lost to follow-up will not be approached either by the Coordinating Center or consortium sites. In the order designated by the program from the study biostatistician until enrollment goals are met, potentially eligible survivors will be sent a letter of approach from their transplant center describing the study, and requesting permission to provide their contact information to NMDP/Fred Hutch. The letter will include a response form, stamped return envelope, study email address, internet URL for the study, temporary participant study ID code and toll-free phone number for survivors to contact NMDP/Fred Hutch to discuss the study or to contact the transplant center Study Coordinator or PI. NMDP will be the default contact for survivors through the study toll-free line, but contacts may be escalated to Fred Hutch as needed based on survivors' questions or concerns about study participation. Initial letter contact will be followed with three phone calls and then one more letter to those who do not respond with a total of up to six phone calls until the participant is reached and indicates interest or declines to participate. Up to three voice messages will be left. After participants return the response form to the consortium sites agreeing that their contact information can be given to NMDP/Fred Hutch study staff, or participants log onto the study internet site and consent, or they contact the Study Coordinators directly by phone or email, all further study activities will be handled by the NMDP and the Coordinating Center. The exception is if survivors from the consortium sites have medical questions. As agreed by the consortium PIs, such questions will be directed by a study investigator at Fred Hutch to the PI at the participant's transplant center.

Enrollment will continue until targeted goals are met, as defined for each targeted outcome in Table 3. We expect this to require 492 participants enrolled in the randomized study.

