## Consent

Before accessing the study questionnaires or any of the secure internet content, the electronic consent form must be agreed to and submitted. Consent will be indicated to include: 1) communication by email and phone (required), access to the secured online internet site (required), and social media (optional), 2) response to self-report assessments, and 3) allowing study access to medical records. After consenting, survivors will be registered for the study with the Fred Hutch study registration office.

Consent, with HIPAA content, will be electronically signed online. Survivors will be able to review and print the consent document before consenting via the online site, as they desire. If survivors have questions or concerns before signing the consent, we encourage them to contact us by phone or by email ([[contact]](mailto:[contact])). Consent will be obtained using forms approved by the Institutional Review Board of Fred Hutch.

*Consenting Information about Treatment Conditions.* Survivors will be told that the research focus is on decreasing distress and increasing health care understanding and actions for people 2 to 5 years after transplant. They will be told that there are two possible groups: 1) full INSPIRE online program and study materials access, with mailed treatment summary and survivorship care plan (TS-SCP) for the survivor and, if they choose to provide names, for their health care providers, with an optional orientation call at 2 weeks and optional self-management calls at 6 weeks; or 2) access to a study website with links to other online resources for survivors, with delayed INSPIRE program access after completion of the 12-month assessment. They will be advised that they will be contacted if we detect severe emotional needs during the course of the study.

The first 100 participants who are approached, with an expected N=20 enrolled for the randomized study, will be treated as "run in" participants to test the website programming and study intervention procedures.

They will be approached and treated as regular participants from survey to data management randomization and intervention. These participants will receive the same access and study experience as later participants, but they will not be included in the outcome analyses or the N=492 sample size. Thus the total enrollment is projected to be N=512.

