## Patient Reported Outcomes (PRO)

### Primary Outcomes

*Cancer and Treatment Distress (CTXD)*. The CTXD is a 22-item inventory of distress or worry related to stressful events for cancer survivors.[25] The measure was developed by the PI from structured interviews with HCT patients, nurses and physicians and has been tested with long-term survivors (N=1978). Testing supports its value as a predictor of health outcomes and it has been used in several RCTs.[6, 148-150] Internal reliability for HCT survivors is  $\alpha = .93$ . There are 6 reliable subscales: uncertainty, health burden, family strain, finances, medical demands, identity.[151]

*Health Care Adherence (HCA)*. The HCA is derived from the Cornell Service Index.[152] We have tested the format with several thousand HCT survivors.[153] Scores are transformed to proportion of HCA recommendations met. For a primary outcome, we use HCA items reflecting adherence to cardiometabolic surveillance (HCA-cardio; 5 items). Additional items measure adherence to subsequent malignancy surveillance (HCA-cancer; 7 items) and will be a secondary endpoint (see below). Items are adjusted for sex and age at which tests are recommended. An item is scored as 'adhered to' if the participant is under the age of recommended test onset. Cut point for determining adherence for each item is based on the frequency of testing recommended in guidelines (annual, every 3 or 5 years). Score is calculated as percentage of tests completed. Since adherence is important to reduce mortality risk, we set the cutoff for not meeting adherence criteria at <80%. In our previous 6-site INSPIRE study, we found 34% not adherent to HCA-cardio surveillance using the above criteria. Validity for HCA-cardio is supported by the following associations ( $p<.01$  for all):

HCA-cardio was higher in those with self-reported high blood pressure, diabetes, history of heart attack, and those told they had cardiomyopathy or atherosclerosis. Discriminant validity is supported by no significant association of HCA-cardio with report of a history of second cancers, osteoporosis, or thyroid problems. The 21 Barriers to HCA items were defined from qualitative patient reports of HCT survivors.[154] With 6 subscales, the overall and subscale reliabilities are all  $\alpha > 0.80$ . Mean score with cut point  $>0.45$  will be used as an Aim 2 predictor. with subscales: Cost, Avoidance, Time, Knowledge, Provider Access, .

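### Table 3 expects 239 HCA-cardio-impaired participants from 492 (48.6%), but the only documented rate is 34%, at which the plan's own enrolment rule needs about 703 randomised

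*Combined protocol and SAP*

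**What the plan says.** Section 12.7, Power Calculations, states: "we expect to enroll a total of 492 subjects in order to attain the 197 and 239 participants needed to meet eligibility criteria". The 197 is for distress (CTXD) and the 239 for cardiometabolic health care adherence (HCA-cardio). Section 12.2 and the baseline-eligibility row of Table 3 repeat both counts. Table 3 then takes 239 down to 172 completers, or 86 per arm.

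A participant counts towards HCA-cardio only if below 80% adherent at baseline (section 12.4). Section 8.2, Primary Outcomes, reports how common that was, with the same cut-off: "In our previous 6-site INSPIRE study, we found 34% not adherent to HCA-cardio surveillance using the above criteria".

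On when enrolment ends, section 7.0 (Intervention Selection and Approach) says "Enrollment will continue until targeted goals are met, as defined for each targeted outcome in Table 3", and then "We expect this to require 492 participants enrolled in the randomized study". The approach forecast in the same section is "Thus we expect we will approach approximately 1358 (36%) of potentially eligible cases". Section 7.3 adds about 20 run-in participants, of whom it says "they will not be included in the outcome analyses or the N=492 sample size", and concludes "Thus the total enrollment is projected to be N=512".

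**The concern.** The first row of the sample size table should be the total N multiplied by the expected share who qualify for each endpoint. For distress it is. For HCA-cardio it is not: the implied share is 48.6%, the documented share is 34%, and nothing in the protocol explains the difference.

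Every planning total rests on this row. If 34% is nearer the truth, 492 randomised participants cannot supply 239 for HCA-cardio. Either recruitment runs well beyond the forecast, or the analysis of one of the two primary endpoints is smaller than the power statement assumes. The text leans towards the first, but the introduction and section 7.3 also give N=492 without qualification, so a reader could take it as fixed.

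**Working it through.** **Inputs.** Randomised N 492; targets 197 and 239; two-sided alpha 0.025 per endpoint; 80% power; effect sizes 0.52 and 0.47; relative risk 1.9 (all section 12.7). Retention 72% of those eligible at baseline (Table 3). Distress prevalence 41% (section 2.1), HCA-cardio non-adherence 34% and HCA-cancer non-adherence 45% (section 8.2). Registry pool 3,765, 26% ineligible after screening, enrolment 51% of non-minority and 40% of minority survivors, at least 15% minority (section 7.0).

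**1. Steps after the entry row.** These reproduce.
- 239 × 0.96 = 229; × 0.75 = 172; ÷ 2 = 86 per arm. Likewise 197 gives 142, or 71 per arm.
- Detectable standardised difference = (2.2414 + 0.8416) × √(2/n): 0.517 at n = 71 and 0.470 at n = 86. The plan states 0.52 and 0.47.

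**2. The entry row.**
- Distress: 197/492 = 40.0%. The documented 41% gives 0.41 × 492 = 202, close to 197.
- HCA-cardio: 239/492 = 48.6%. The documented 34% gives 0.34 × 492 = 167.
- Rates for other measures do not give 239 either: 41% gives 202 and 45% gives 221.
- Chance does not bridge the gap. If the true rate were 34%, the binomial probability of 239 or more among 492 is about 2 × 10⁻¹¹.

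**3. Randomised N needed to reach 239** (239 ÷ prevalence, rounded up; 34% is documented, the middle two rates are assumptions, and the last is the plan's implied rate).

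| HCA-cardio non-adherence | N needed |
|---|---|
| 34% | 703 |
| 40% | 598 |
| 45% | 532 |
| 48.6% | 492 |

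At 34%: 703/492 = 1.43, and 703 + 20 run-in = 723.

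**4. Approaches at 703 randomised.** Three ways of scaling the plan's own yield:
- Run-in approaches held at 100: (1,358 − 100)/492 × 703 + 100 = 1,897.
- Simple proportion: 1,358/492 × 703 = 1,940.
- Section 7.0 rates: 703 ÷ (0.51 × 0.85 + 0.40 × 0.15) ÷ 0.74 = 1,925. The same formula at 492 gives 1,347, near the stated 1,358.

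These differ mainly in how they treat the run-in and are not independent confirmations. All give 50% to 52% of the 3,765, against the stated 36%.

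**5. Distress at 703.** At the Table 3 rate of 40%: 281 eligible; 281 × 0.72 ÷ 2 = 101 per arm; detectable difference about 0.43. At 41%: 288 eligible and about 104 per arm.

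**6. Only if enrolment stops at 492, at 34%.** 167.3 × 0.72 ÷ 2 = 60 per arm.
- Continuous version: power for 0.47 is Φ(0.47 × √30 − 2.2414) = Φ(0.33) = 63%. A difference of 0.56 is needed for 80%.
- Binary version: the plan gives no control-arm success rate. With the pooled-variance normal formula, 80% power for a relative risk of 1.9 at 86 per arm implies a control rate of about 25%. Power by assumed control rate:

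| Control rate (assumed) | 86 per arm | 60 per arm |
|---|---|---|
| 20% | 64% | 47% |
| 25% | 80% | 63% |
| 30% | 92% | 78% |
| 35% | 98% | 90% |

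**The case against.** The strongest reply is that 34% is not a like-for-like figure. It comes from the earlier six-site study, which recruited survivors 2-10 years after transplant (section 2.2); this trial takes them at 2-5 years (section 4.1). It was also scored by guideline interval, which for some tests is three or five years, whereas the Hypothesis 1 analysis plan counts only the past 12 months. If the shorter window also applies at baseline, fewer tests would count and non-adherence would exceed 34%, perhaps approaching 48.6%. The 41% for distress, by contrast, is explicitly a 2-5 year rate. This stands: 703 is conditional on 34%. It does not supply the missing source, however, and it exposes a second mismatch, because the two sections define the adherence window differently.

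The next reply is that the enrolment rule protects the trial. Recruitment continues to 239 whatever the prevalence, the registry pool is large enough, and participation by stratum is reviewed annually (section 7.5). This stands as regards power. The review could reveal a shortfall during accrual, but it does not correct the forecast.

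It can also be said that no stated calculation is wrong, since 239 is never derived from 34%. That is fair: this is an unsourced planning assumption in conflict with the plan's only evidence. Lastly, exceeding 197 for distress is a surplus that leaves the stated detectable effect conservative. That is also right; the column would misdescribe the expected sample without weakening the analysis.

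**Conclusion.** The concern holds as an unreconciled conflict between the HCA-cardio entry in Table 3 and the rate in section 8.2. The 492 forecast does not deliver 239 at the only rate the protocol documents. Under the section 7.0 rule, the shortfall at 34% is about 211 randomised participants and between 539 and 582 approaches (1,897 to 1,940, less 1,358). At assumed rates of 40% and 45% the required N is still 598 and 532.

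Confidence in the mismatch is high. The size of its effect depends on the true non-adherence rate in 2-5 year survivors under whichever recall window applies, and the documents do not give that rate. Power for HCA-cardio is at risk only if 492 is treated as a ceiling, which no section says. The binary power figures for that case also rest on assumed control rates.

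**What to change.** 1. State the source of the HCA-cardio entry rate in Table 3. Use 34%, or another sourced rate that matches the 2-5 year population and the recall window of the endpoint, and say which window applies at baseline and at 12 months.
2. Confirm that the section 7.0 rule governs the end of enrolment. Then restate the expected randomised N, total enrolment and number approached wherever they appear: the introduction, sections 7.0 and 7.3, Table 2, and sections 12.2 and 12.7. Bring the distress column of Table 3 to the same N, noting that it exceeds its minimum.
3. Only if 492 is meant as a cap, say so and restate the HCA-cardio number per arm, power and detectable effects, with the assumed control-arm rate.

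The change is to wording only. The price is a larger recruitment forecast, with the time and budget that follow, or under a cap a less favourable detectable effect. If a sound source for 48.6% exists, a sentence citing it would resolve the conflict over the entry rate and 492 could stay.
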